Three responder rates will be utilized: 50%, 75% and 100%. A responder is a subject who achieves a $\geq 50\%$ reduction, $\geq 75\%$ reduction, or 100% reduction in migraine days, respectively. These reductions will be evaluated by comparing the baseline frequency of migraine days to the migraine frequency in four week intervals. The same analyses will be conducted for headache days.

Results from these four week intervals will be combined to produce 12 and 24 week responder endpoints. The Weeks 1-4, 5-8, and 9-12 change from baseline measures are averaged, and the average value is compared to baseline. A percent change from baseline is determined, which is used to determine the responder status. A 75% migraine responder will be a subject who achieves the specified percent reduction in migraine days within these intervals based upon the average change from baseline measures. A 50% migraine responder will be similarly defined.

A 100% migraine responder rate over Weeks 1-12, 13-24 and 1-24 is the average of the 100% responder rate for four week intervals that make up these intervals. Hence, the 100% migraine responder rate over weeks 1-12 is the average of the 100% migraine responder rates in Weeks 1-4, 5-8 and 9-12 for the treatment arm.

Time to First Migraine

Time to the first migraine after dosing will be analyzed based upon the migraine data entered into the eDiary.

Migraine Hours/Headache Hours

Migraine hours are the sum of the duration of migraines within four week intervals, and the average four week duration within 12 and 24 week intervals. Headache hours are similarly defined but include all headaches. Subjects with no migraines/headaches will have a duration of zero.

Acute Medication Usage

The percent of migraines and headaches with acute medication use will be summarized.

Subjects with no migraines/headaches will be included with a rate of zero.

Acute Migraine Medication Usage

The number of days that subjects used acute migraine medication (i.e. triptan or ergotamine) will be summarized in 4, 12, and 24 week intervals. The 12 and 24 week results will be the average of the individual 4 week results that make up those wider intervals (e.g. the secondary endpoint of Weeks 1-12 will be the average of the Weeks 1-4, 5-8, and 9-12 results). The change from baseline for these measures will be the difference between the post baseline interval and baseline.

Percentage of subjects with a migraine on the day after dosing

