The frequency of migraine days is the number of migraine days within four week intervals and the average four week frequency in twelve and twenty-four week intervals. Change from baseline is the difference in frequency between baseline and the counts within these four week intervals. The 12 and 24 week change is the difference in the frequency between baseline and the average of the 4 week intervals. The percent change is 100 times the ratio of the change and the baseline frequency. Similar measures will be produced based upon headache frequency.

Migraine/ Headache Responder Rate

Three responder rates will be utilized: 50%, 75% and 100%. A responder is a subject who achieves a $\geq 50\%$ reduction, $\geq 75\%$ reduction, or 100% reduction in migraine days, respectively. These reductions will be evaluated by comparing the baseline frequency of migraine days to the migraine frequency in four week intervals. The same analysis will be conducted for headache days.

Results from the four week intervals will be averaged to produce 12 and 24 week responder endpoints. The Weeks 1-4, 5-8, and 9-12 change from baseline measures are averaged, and the average values are compared to baseline. A 75% migraine responder will be a subject who achieves the specified percent reduction in migraine days within these intervals based upon the average change from baseline measures. Specifically, the 75% 12 weeks responder status is defined as,

$$75\% \text{ Responder Status} = \begin{cases} 1 & \text{if } \frac{\text{ave}(\Delta_{\text{Month } 1}, \Delta_{\text{Month } 2}, \Delta_{\text{Month } 3})}{\text{Baseline}} \leq -0.75 \\ 0 & \text{if } \frac{\text{ave}(\Delta_{\text{Month } 1}, \Delta_{\text{Month } 2}, \Delta_{\text{Month } 3})}{\text{Baseline}} > -0.75 \end{cases}$$

A 50% migraine responder will be similarly defined.

The 100% migraine responder rate over Weeks 1-12, 13-24, and 1-24 are calculated by averaging the subjects 100% responder status (i.e. 1 if responder and 0 if not). So a subject who is a 100% responder for month 1 but not 2 and 3 will have a 100% responder rate of 33% (1+0+0/3).

Percentage of Subjects with a Migraine on the Day after Dosing

The percent of subjects with a migraine on the day after dosing will be summarized. For subjects who do not complete the diary on this day the missing data rule outlined in Section 2.7.2 will be used.

Reduction in Migraine Prevalence from Baseline to Week 4

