3.4.2. Responder Rates

The 50%, 75% and 100% responder rates will be determined as outlined in the missing data Section 2.7.2 and the endpoint definition in Section 2.2.2. The number of subjects who are responders and the rate (full analysis population as the denominator) will be summarized for each treatment group at each 4, 12, and 24 week interval. The difference in rates and associated confidence interval will also be produced. These confidence intervals will be calculated based upon the normal approximation for two independent proportions. Stratification will not be used for these intervals. The SAS procedure, Proc Freq, will be used to calculate these confidence intervals. Any interval for which the normality assumption is questionable (i.e. $np < 5$ or $nq < 5$) will be flagged.

Plots of the percent of responders across time, for each response level, will be produced. These plots will use the four week responder rates.

A p-value for the difference in rates for the key secondary endpoints will be based upon the CMH test outlined in Section 2.5.

Should the as randomized and ‘true’ values for the stratification factors differ, the as randomized values will be used within these CMH tests. The SAS procedure, Proc Freq, will be used to calculate this p-value. Cumulative distribution of the responder rate will be plotted.

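### The two-proportion interval, responder count and small-count flag in SAP 3.4.2 do not fit the 12- and 24-week 100% responder rate, which is a per-subject average

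*SAP*

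**What the plan says.** SAP 2.2.2 defines the rate over Weeks 1-12, 13-24 and 1-24 by averaging within the subject: "The 100% migraine responder rate over Weeks 1-12, 13-24, and 1-24 are calculated by averaging the subjects 100% responder status". Its worked example leaves no doubt that the score is fractional: "So a subject who is a 100% responder for month 1 but not 2 and 3 will have a 100% responder rate of 33" percent. Protocol 12.1.2 describes the same quantity at arm level: the rate "is the average of the 100% responder rate for four week intervals that make up these intervals". With the same subjects in every interval, the two definitions give the same point estimate. The 12-week 75% status, by contrast, is written in SAP 2.2.2 as a 1-or-0 variable, and the 50% status is defined similarly.

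SAP 3.4.2 then handles all three levels together. It opens with "The 50%, 75% and 100% responder rates will be determined as outlined in the missing data Section 2.7.2", and the reporting rule is "The number of subjects who are responders and the rate (full analysis population as the denominator) will be summarized for each treatment group", at every 4-, 12- and 24-week interval. On the interval it says "These confidence intervals will be calculated based upon the normal approximation for two independent proportions" and "The SAS procedure, Proc Freq, will be used to calculate these confidence intervals". Stratification is not used, and any interval with np or nq below 5 is flagged. No exception is made for the averaged 100% rate. SAP 3.4.3 promises intervals for the remaining secondary endpoints but gives no other formula.

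**The concern.** A variable with values 0, 1/3, 2/3 and 1 (or sixths over Weeks 1-24) has no number of responders, its variance is not p(1-p), and np is not a binomial count. It also does not form the two-level table that a two-proportion interval needs, so the programmer has to choose how to enter it. Three choices are open, with different results:

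- Put the mean score into the binomial formula with n equal to subjects.
- Enter each subject-month as a separate 0/1 row.
- Cut the score into responder and non-responder, which changes the endpoint.

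At stake is the interval printed beside a named secondary endpoint, the 100% migraine responder rate for Weeks 1-12. The SAP adapts its method to fractional values elsewhere: in 2.5.2 the day-after-dosing endpoint gets an extended CMH test because imputed values can lie between 0 and 1.

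**Working it through.** **Inputs from the documents.** 350 subjects per group (SAP 1.5); full analysis population as denominator (SAP 3.4.2); number of 4-week intervals K = 3 for Weeks 1-12 and 13-24, and K = 6 for Weeks 1-24 (SAP 2.4, Table 4).

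**Assumed inputs.** SAP 3.4.2 states no confidence level; 95% is assumed from the two-sided 5% alpha in SAP 2.5.1. The documents give no 100% responder rates and no between-month correlation rho, so 10% vs 5% and a range of rho are used for illustration.

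**The plan's own figure.** There is none for this endpoint. The only responder-rate planning figure is 90% power for 20% vs 31% with 350 per arm (SAP 1.5). The usual two-proportion calculation gives 91.8%, and 90% power needs 328 per arm (346 with continuity correction), so that figure is consistent. Nothing below depends on it.

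**Direction, with subjects as the denominator.** Let Y be a subject's average, between 0 and 1, with mean p. Then Y² ≤ Y, so

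Var(Y) = E(Y²) − p² ≤ p − p² = p(1−p).

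Equality holds only if every subject scores exactly 0 or 1, that is, has the same status in all months. This needs no assumption about rates or correlation.

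**Size.** With equal monthly rates and a common between-month correlation rho,

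Var(Y) = p(1−p) × [1 + (K−1)rho] / K.

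The binomial half-width is 1.96 × sqrt(0.10×0.90/350 + 0.05×0.95/350) = 1.96 × 0.01982 = 3.88 points. The correct half-width is 3.88 × sqrt([1 + (K−1)rho]/K):

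| rho | K = 3: correct half-width (points) | Printed interval wider by | K = 6: correct half-width (points) | Printed interval wider by |
|---|---|---|---|---|
| 0.3 | 2.84 | 37% | 2.51 | 55% |
| 0.5 | 3.17 | 22% | 2.97 | 31% |
| 0.7 | 3.47 | 12% | 3.36 | 15% |
| 1 | 3.88 | 0% | 3.88 | 0% |

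At rho = 0.9 the excess is 3.5% (K = 3) and 4.4% (K = 6). At rho = 0.5 the nominal 95% interval covers 98.4% (K = 3) and 99.0% (K = 6).

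**Check with unequal monthly rates.** Simulations used 350 per arm and latent correlations of 0.3 to 0.95. Mean rates were 5% vs 10% for K = 3 and about 7% vs 13% for K = 6. The binomial interval was 12% to 57% wider than the means-based one for K = 3 and 16% to 93% wider for K = 6, with coverage of 97.4% to 100%. The means-based interval covered 94.0% to 95.5%.

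**Direction, with subject-months as independent rows.** The point estimate is unchanged, but the half-width becomes 3.88/sqrt(3) = 2.24 points for K = 3. That is below every K = 3 value in the table. At rho = 0.5 coverage would be about 83% (K = 3) and 71% (K = 6).

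**The case against.** The strongest defence is that little follows from this. The 100% rate is listed under other secondary endpoints. It is absent from the testing sequence in SAP 2.3, where all analyses outside the sequence are called exploratory. SAP 2.5.3 plans only summary statistics for it, and SAP 3.4.2 reserves CMH p-values for the key secondary endpoints. The 50% and 75% rates, including every responder rate in the testing sequence, are binary and correctly handled, as are the 4-week 100% rates. On the subject-level reading the error is conservative. All of this stands, and it limits the weight of the point.

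A second objection concerns direction. A reader might infer that the printed interval is bound to be too wide. The documents do not go that far: the wording "the rate (full analysis population as the denominator) will be summarized for each treatment group at each 4, 12, and 24 week interval" favours subjects as n, but it describes the reported rate, and nothing says how a fractional score enters Proc Freq. With subject-month rows the error reverses. What is established is the misfit; too wide is conditional on subject-level n.

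Third, the size rests on assumed rates and rho, and the excess is small when subjects rarely change status. That is true, so the widths are illustrations, not predictions.

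Finally, a normal interval on scores that are mostly zero can itself be poor when responders are very rare. Coverage was satisfactory at the rates simulated, but removing the binomial flag leaves no sparse-data check, and the fix should supply one.

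**Conclusion.** The point holds as a mismatch between definition and method, confined to the 100% rates over Weeks 1-12, 13-24 and 1-24. With the full analysis population as the denominator, the stated interval is too wide in every case except identical status in all months for every subject. The printed half-width of 3.9 points compares with about 2.8 to 3.5 over 12 weeks and 2.5 to 3.4 over 24 weeks, given the assumed 10% vs 5%, a 95% level and rho of 0.3 to 0.7. The direction under that reading is a mathematical fact; the size is not fixed by the documents.

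The documents do not support the inference that any hypothesis test, step of the testing sequence or power figure is affected, or that the protocol and SAP disagree on what the rate is. Under the averaging definition the point estimate is also unchanged. This is a minor correction, best settled before unblinding so that the choice is not left to programming.

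**What to change.** In SAP 3.4.2, exempt the 100% responder rate over Weeks 1-12, 13-24 and 1-24 from the proportion format:

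- Report the mean of the subject-level averages per arm. Give an unstratified normal interval for the difference in means from their observed variance, as SAP 3.4.1 already does for migraine days, and state the confidence level.
- Drop the responder count and the np/nq flag for these rows. A simple replacement check is to flag any arm in which fewer than 5 subjects have a score above zero, or fewer than 5 a score below one.
- If a count is wanted, report subjects who are 100% responders in every 4-week interval as a separate, labelled item. It is a different quantity and should not replace the defined rate.

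The cost is a short SAP revision and a few lines of code. No data collection, sample size, test or other responder-rate output changes.

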subjects record if they took acute migraine medication on that day. In addition to the evening report the eDiary captures headaches as individual events with a start and end time. It is these headache reports which are used to derive the migraine and headache endpoints. Subjects are allowed to tell the eDiary about headaches that started today and yesterday and are unable to record headaches that started before yesterday. Headaches must be entered in order and at the completion of the headache the subject answers questions about the headache that allow the headache to be classified as a migraine or non-migraine headache as outlined in Section 2.2.2. The eDiary data from the 28 days following screening visit will be used to determine eligibility criteria, and the baseline migraine and headache results.

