The number of days that subjects used acute migraine medication (i.e. triptan or ergotamine) will be summarized in 4, 12, and 24 week intervals. The 12 and 24 week results will be the average of the individual 4 week results that make up those wider intervals (e.g. the secondary endpoint of Weeks 1-12 will be the average of the Weeks 1-4, 5-8, and 9-12 results). The change from baseline for these measures will be the difference between the post baseline interval and baseline.

Migraine Free Days

The number of days between migraines are classified as migraine free days. Multiple migraine free intervals will exist for each subject. The Migraine Free Days endpoint will measure the length of these intervals. For these calculations all days between recorded migraines will be considered migraine free.

Patient Global Impression of Change (PGIC)

The PGIC includes a single question concerning the subject's impression of the change in their disease status since the start of the study. Seven responses are possible: Very Much Improved, Much Improved, Minimally Improved, No Change, Minimally Worse, Much Worse, Very Much Worse.

SF-36 Health Survey (SF-36 v2.0)

The SF-36 v2.0 is a health survey containing 36 questions consisting of eight scaled scores to measure quality of life over the past 4 weeks. The eight sections measured are vitality, physical functioning, bodily pain, general health perceptions, physical role functioning, emotional role functioning, social role functioning, and mental health. These domains are combined into the mental component score and the physical component score. Scoring software utilizing the 2016 norm-based scoring algorithm will be used to calculate the scaled score for each of the eight sections.

EQ-5D-5L

The EQ-5D-5L is a descriptive system of health-related quality of life states consisting of five dimensions/questions (mobility, self-care, usual activities, pain/discomfort, anxiety/depression) each of which can take one of five responses. The responses record five levels of severity (no problems/slight problems/moderate problems/severe problems/extreme problems) within a particular EQ-5D dimension. The EQ-5D-5L additionally includes a VAS scale. Each item will be summarized separately.

Headache Impact Test (HIT-6 v1.0)

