2.5.4. Tertiary Efficacy Analyses

Tertiary endpoints will be summarized with descriptive statistics by treatment group. For the Migraine Free Days endpoint the summary measures will be the longest migraine free interval that started within the first two weeks following treatment.

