2.7.2. Handling of Dropouts or Missing Data

Summary statistics will be reported based upon observed data except for the imputation outlined below. Additionally, if the start date of an AE or concomitant medication is incomplete or missing, it will be assumed to have occurred on or after the infusion of trial medication, except if an incomplete date (e.g., month and year) clearly indicates that the event started prior to treatment.

Subjects who do not complete the eDiary daily will have missing data. It is expected that most missing diary data will be sporadic.

Missing Headache End Date and Time

If the end date and time for a headache recorded in the eDiary is missing the headache end date will be set to the earlier of 23:59 on the day before the next reported headache or 23:59 on the last entry reported into the diary (i.e. the last evening report or if no evening report was completed after the start of the headache 23:59 on the day the headache started). Headaches that are not reported as stopped by the subject are missing the answers to the questions that allow for the determination of whether the headache was a migraine or not. In this population most headaches are migraines. Hence, these headaches with missing 'end' information will be classified as migraines.

Missing Data Rule 1

If the eDiary has been completed at least 21 days in a 28 day interval, then a normalization procedure will be used. The results will be normalized to 28 days by multiplying the observed results by the inverse of the completion rate (e.g. if a subject does not complete the eDiary on 5 days they will have completed the diary on 82% of the days and the normalized results will be the observed results times 1.22).

For the tertiary endpoints (except migraine free days), only Missing Data Rule 1 will be used and the denominators for will reflect the number of subjects who completed the eDiary 21 or more days in the 28 day interval. For Migraine Free Days no imputation will be used.

Missing Data Rule 2

If the eDiary has been completed on less than 21 days in the 28 day interval then the results for the 28 day interval will be a weighted function of the observed data for the current four week interval and the results from the previous interval. The weights will be proportional to how many days the diary was completed and will provide greater weight for higher completion rates. Specifically, the results will be derived as

$$28 (W X_c + (1 - W) X_p),$$

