3.3.6. Clinical Trial Treatment

Total volume infused, number of infusions and reason for dose interruption will be listed as well as summarized in a table.

3.3.7. eDiary Compliance

The rate of missing eDiary data within each four week interval, which is defined as $(\text{number of days with missing eDiary data} / 28) * 100$, will be summarized descriptively. A day will be considered as missing if the subject did not interact with their eDiary and the subject did not experience a headache on that day.

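### Migraine Free Days counts multi-day diary gaps as migraine-free time, and read literally it gives no value to subjects with no, one or only late migraines after dosing

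*SAP*

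**What the plan says.** SAP 2.2.2 defines the endpoint: "The number of days between migraines are classified as migraine free days". It adds that "Multiple migraine free intervals will exist for each subject" and that "For these calculations all days between recorded migraines will be considered migraine free". SAP 2.5.4 makes the summary measure "the longest migraine free interval that started within the first two weeks following treatment". SAP 2.7.2 exempts the endpoint from the diary missing-data rules: "For Migraine Free Days no imputation will be used".

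Four other places bear on it:

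- SAP 2.2.1 says that subjects "are unable to record headaches that started before yesterday".
- SAP 3.3.7 already defines a missing diary day: "A day will be considered as missing if the subject did not interact with their eDiary" and had no headache that day. The Migraine Free Days rule does not use this definition.
- SAP 2.7.2 says that headaches entered without end "information will be classified as migraines".
- SAP 3.4.2.3 censors time to first migraine at the last diary entry. No such rule is given for Migraine Free Days.

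The SAP does not say whether dosing opens an interval, what to do with an interval that no migraine closes, or what value a subject with fewer than two migraines receives.

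**The concern.** Two features of the definition pull the result away from what it is meant to show.

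First, the rule rests on recorded migraines. A day without diary data inside an interval counts as migraine free, so although imputation is ruled out, the most favourable value is in effect assigned. The SAP's other diary rules do not do this: Rule 1 scales up for missed days, Rule 2 borrows from the previous interval, and the prevalence endpoints use the subject's own Weeks 1-4 rate. Taking the longest interval then tends to select the gap.

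Second, an interval between migraines needs a migraine at both ends. The statement that every subject has several intervals sits badly with the rest of the SAP, which plans 100% responder rates and Kaplan-Meier percentages migraine free out to Week 24. The subjects most likely to have no interval are those with the fewest migraines.

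What is at stake is how an added descriptive measure is interpreted. SAP section 4 says it was added because it may show treatment benefit in a clinically meaningful way.

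**Working it through.** The documents give no figure for this endpoint, so there is none to reproduce. The rule was applied literally to worked cases, then simulated. Migraine rates and missing-diary rates below are assumptions, with days treated as independent over 168 diary days.

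**Worked cases**

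- Migraines on Days 1, 3, 5 and so on to Day 27, full diary: longest interval 1 day.
- Same subject, Days 6 to 12 not recorded: the migraines on Days 7, 9 and 11 are lost, and the interval runs from the Day 5 migraine to the Day 13 migraine, which is 13 − 5 − 1 = 7 days. Next-day entry does not help, because on Day 13 only a headache that started on Day 12 or 13 can be entered.
- No migraine after dosing: no interval.
- One migraine, on Day 2: no closed interval.
- First migraine on Day 20, next on Day 60: no interval starts in the first two weeks.

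**Simulation with every missed day lost** (6,000 subjects per scenario, last start Day 14; means are over subjects with a value)

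| Migraine days per 28 | Full diary | 3/28 of days missing at random | 7/28 missing at random | One 7-day gap starting Days 1-14 | No value, full diary |
|---|---|---|---|---|---|
| 16 | 2.9 | 3.4 | 4.1 | 8.1 | 0.1% |
| 8 | 6.2 | 6.8 | 7.9 | 10.5 | 1.0% |
| 4 | 10.8 | 11.9 | 13.5 | 14.9 | 11.8% |
| 2 | 18.9 | 20.2 | 23.2 | 22.8 | 36.5% |

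Gaps can also remove a value: at 4 per 28 the no-value share rises from 11.8% to 26.9% with the 7-day gap.

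**Allowing next-day entry.** If every subject back-enters, a missed day is lost only when the following day is missed too. With 10% of days missed at random, 0.10 × 0.10 = 1% of days are lost; with 30%, 0.30 × 0.30 = 9%. At a 30% daily migraine probability the mean longest interval is about 5.8 days with a full diary, about 5.8 to 6.3 with 10 to 30% of days missed at random, and about 9.4 with one early 7-day gap. The inflation comes from runs of missed days.

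**Share with no value, full diary.** An interval starts on a day without a migraine that follows a day with one. With daily probability p and q = 1 − p, none starts among n counted days only if those days are all migraine-free days followed by an unbroken run (possibly empty) of migraine days:

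P(no value) = Σ qᵏpⁿ⁻ᵏ (k = 0 to n) = (qⁿ⁺¹ − pⁿ⁺¹)/(q − p).

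This ignores intervals that never close by Day 167, which are negligible at this rate. At p = 0.15 the pⁿ⁺¹ term is also negligible and q − p = 0.70:

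- Days 0-14, n = 15: 0.85¹⁶/0.70 = 0.0743/0.70 = 10.6%.
- Days 0-13, n = 14: 0.85¹⁵/0.70 = 0.0874/0.70 = 12.5%.
- Days 1-13, n = 13: 0.85¹⁴/0.70 = 0.1028/0.70 = 14.7%.

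As a check on the table, p = 4/28 with n = 15 gives (6/7)¹⁶/(5/7) = 0.0849/0.7143 = 11.9%, against 11.8% simulated. For scale, a 75% reduction from 17 migraine days, the stratification cut-point, leaves 17 × 0.25 = 4.25 per 28 days, a daily probability of about 15%.

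**The case against.** Much of the case on the other side stands.

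- **A missed diary day is not a missed migraine.** Headaches are logged as events separate from the evening report, yesterday's headache can still be entered, and a missed day without a migraine changes nothing. SAP 2.7.2 expects most missing data to be sporadic. The rule for headaches with no end entry works the other way and shortens intervals. All of this is right, and it confines the first problem to multi-day gaps.
- **The no-value result is an inference.** No sentence excludes anyone, and the SAP 2.5.4 wording could include an interval that opens at dosing. This also stands: for these subjects the SAP is silent, and a programmer would have to choose.
- **Bias between arms.** A reader might infer that the endpoint favours ALD403 through poor compliance, or penalises it by dropping its best responders. The documents support neither. The trial is double-blind, nothing suggests that compliance differs by arm, the two effects oppose each other, and no net effect on a treatment difference has been calculated.
- **Importance.** The endpoint is declared as an exploratory addition and lies outside the testing sequence. Migraine-free benefit is also covered by time to first migraine, with censoring, and by the 100% responder rate.

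The objection does not remove the stated rule that unrecorded days between migraines are migraine free.

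**Conclusion.** The point holds in a limited form. By a stated rule, a multi-day early diary gap that hides migraines is counted as a migraine-free interval. One 7-day gap moves the mean longest interval from about 5.8 to about 9.4 days at a 30% daily probability with next-day entry. Sporadic missed days add at most about half a day under the same assumptions.

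Separately, on the literal reading of the definition, roughly 11 to 15% of subjects at a constant 15% daily probability have no value, and the share grows as migraines become rarer. It would be wrong to say that the SAP expressly excludes the best responders; it leaves their value undefined.

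The sizes rest on assumed rates, independent days and, where stated, full use of next-day entry. They show direction and rough scale only. No primary or key secondary analysis is touched, so this is a minor correction.

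**What to change.** Amend SAP 2.2.2 and 2.5.4, ideally before unblinding:

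1. Let the first interval open at dosing. With a full diary this cuts the simulated no-value share from 11.8% to 0.0% at 4 migraine days per 28, and from 60.2% to 0.2% at 1 per 28.
2. Run an interval with no closing migraine to the last diary entry and flag it as censored. Every subject with post-dose diary data then has a value, including those with no migraine.
3. Do not count days that meet the SAP 3.3.7 definition of missing as migraine free. Either leave them out of the interval length or end the interval there; state which. Report the as-recorded version as a sensitivity summary.
4. If Kaplan-Meier is wanted, apply it to one defined interval per subject. The method in SAP 3.4.2.3 does not carry over to the longest of several intervals, some of them censored: a subject may have one interval censored at 3 days and another complete at 8.
5. Remove the statement that every subject has multiple intervals.

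The cost is SAP wording and minor programming. The downside is that intervals containing missing days become shorter. Long intervals are more likely to contain one, so they are affected most; this is why the as-recorded version should be kept alongside.
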